### 9.1.3 Primary Adverse Event

A Primary AEs is an event listed in Table 9.1.3A which occurs within the first week (7 days) following an ablation procedure.

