Stroke/Cerebrovascular Accident (CVA)	
Diagnosis:
 
 
-Rapid onset of a focal or global neurological deficit with at least one of the following: change in level of consciousness, hemiplegia, hemiparesis, numbness or sensory loss affecting one side of the body, dysphasia or aphasia, hemianopia, amaurosis fugax, or other neurological signs or symptoms consistent with stroke.
 
-Duration of a focal or global neurological deficit <math>\geq 24</math> h; or <math>< 24</math> h, if therapeutic intervention(s) were performed (e.g. thrombolytic therapy or intracranial angioplasty); OR available neuroimaging documents a new hemorrhage or infarct; or the neurological deficit results in death.
 
-No other readily identifiable non-stroke cause for the clinical presentation (e.g., brain tumor, trauma, infection, hypoglycemia, peripheral lesion, pharmacological influences).†
 
-Confirmation of the diagnosis by at least one of the following: Neurology or neurosurgical specialist; Neuroimaging procedure (MR or CT scan or cerebral angiography); Lumbar puncture (i.e., spinal fluid analysis diagnostic of intracranial hemorrhage)
 
 
Definition:
 
Stroke: (diagnosis as above, preferably with positive neuroimaging study)
 
 
Minor—Modified Rankin score <math>< 2</math> at 30 and 90 days††
 
Major—Modified Rankin score <math>\geq 2</math> at 30 and 90 days
 

Transient Ischemic Attack	
New focal neurological deficit with rapid symptom resolution (usually 1 to 2 h), always within 24h; neuroimaging without tissue injury.

Phrenic Nerve Paralysis	
Absent phrenic nerve function as assessed by a sniff test, associated with symptoms of dyspnea and orthopnea (diagnosed by chest x-ray). A phrenic nerve paralysis is considered to be permanent when it is documented to be present 12 months or longer following ablation. Under this protocol, diaphragmatic paralysis/phrenic nerve palsy will be considered a Primary AE if specified symptoms have not improved at the 3- month visit

Primary Adverse Event	Description / Criteria
Pulmonary Vein Stenosis*	A reduction of the diameter of a PV. Severe PV stenosis ( $\geq 70\%$ reduction in the diameter of the PV) will be considered a primary adverse event and major complication of AF ablation.

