9 SAMPLE SIZE JUSTIFICATION

A Bayesian adaptive design will be utilized to select the final sample size of the trial. The sample size for the study is mainly driven by the primary safety endpoint. Sample size selection interim analyses will be performed when the mITT Population reaches 80, 130, and 180 subjects. Safety outcomes at 30 days will be used as a proxy for the primary safety endpoint at each

Biosense Webster, Inc

interim for determining the sample size. The predictive probabilities for the primary safety endpoint success will be used to determine whether the sample size at the time of the interim analysis will be sufficient or if the trial will continue to the full sample of 230. The final stopping sample size of 230 was determined by fixed design power calculations for the primary safety endpoint.

Trial simulations were performed to estimate the Type-I error rate and the power for the success of the safety endpoint under a range of assumptions for the true safety rate and the assumed enrollment schedule. It is assumed that the attrition rate for the study will be negligible. For accrual rates of 1.7, 3.4, 5.1, 8.5, 11.9, 17, 20.4, 23.8, 25.5, 25.5, 25.5, 25.5, 25.5, and 25.5 patients per month for months 1 to 15 respectively, and true safety rates of 0.0% to 9.0%, the power for showing success for the primary safety endpoint is estimated to be greater than or equal to 80.0%. For a safety rate of 9.5% this power decreases to approximately 73.0%. Based on the feasibility study results referenced in the study protocol, it is unlikely that the safety event rate is higher than 9.0%. The posterior probability of the safety rate being less than or equal to 9.0% is estimated to be 0.886. Therefore, the study is expected to be sufficiently powered for the primary safety endpoint. With an assumed true effectiveness rate of 96.0% and a performance goal of 80.0%, a minimum of 80 subjects will provide higher than 99.0% power for meeting the primary effectiveness endpoint. As a result, the power estimates for the primary safety endpoint closely estimate the overall power of the study.

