11.4.2 Primary Safety Endpoint

The PAE rate will be compared to a performance goal of 15% by using the exact test for a binomial proportion at a one-sided significance level of 5%. If the one-sided 95% upper confidence bound for the primary safety rate is less than the performance goal of 15%, the study will be considered to have demonstrated safety.

The Modified Intent-To-Treat (mITT) population will be used as the analysis population for the primary safety endpoint. Subjects without full follow-up required per protocol for the safety

endpoint assessment will be excluded in the primary analysis unless they have experienced a PAE. The primary safety endpoint will also be analyzed in the roll-in subjects.

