11.4.4 Handling of Missing Data

Interim Analysis:

At the time of each interim analysis, some subjects will not have completed the full 30-day follow-up for their safety evaluation. The number of failures for the primary safety endpoint in subjects with incomplete information will be assumed to follow a beta-binomial distribution. The predicted number of failures for the primary safety endpoint will be estimated from these beta-binomial distributions for estimating the predictive probability of success for the safety endpoint.

Final Analysis:

The reasons for missingness, if available, will be listed for subjects with missing data. Patients with missing effectiveness data will be excluded from the primary effectiveness analysis.

Subjects without full follow-up required per protocol for the safety endpoint assessment will be excluded in the primary analysis unless they have experienced a PAE. Sensitivity analyses for missing data will be performed to assess the impact of missing values on the primary safety outcome and are described in the section 11.4.5.

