12 APPENDIX – ADAPTIVE DESIGN SIMULATION REPORT

Adaptive Design Simulation Report

1. Study Design

This clinical investigation is a prospective, multicenter, single arm clinical evaluation utilizing the Biosense Webster multi-electrode radiofrequency balloon catheter and the Biosense Webster multi-electrode circular diagnostic catheter. The sample size for the study is primarily driven by the safety endpoint. An adaptive Bayesian design¹ will be used to determine the sample size based on the safety endpoint alone. The primary safety and effectiveness endpoints will be evaluated using exact tests for binomial proportions at a one-sided 5% significance level.

The null and alternative hypotheses are for primary effectiveness endpoint are:

Hypothesis $H_0: P_E \leq 0.80$

$H_a: P_E > 0.80$

where P_E is the Proportion of patients with acute procedural success defined as confirmation of entrance block in treated PVs after adenosine and/or isoproterenol challenge. The null and alternative hypotheses for the Primary Safety Endpoint are:

Hypothesis $H_0: P_S \geq 0.15$

$H_a: P_S < 0.15$

where P_S is the rate of Primary Adverse Events

2. Sample Size Justification

The study will utilize an adaptive design. The methods described in Broglio et al.^[1] will be used to determine the sample size based on the safety endpoint alone. Sample size selection interim analyses will be performed when 80, 130, and 180 patients are available for the primary safety endpoint analysis. Predictive probabilities for trial success will be used to determine whether the sample size at the time of the interim analysis will be sufficient or if the trial will continue to the full sample of 230. Power for the effectiveness endpoint assessment is >80% at all sample sizes ≥ 80 subjects.

The final stopping sample size of 230 was determined by power calculations for the primary safety endpoint. Based on a performance goal of 15% for the primary safety endpoint and an anticipated rate of at most 9.5% for the primary safety endpoint, 230 subjects will be sufficient to obtain at least 80% power at a one-sided significance level of 5%.

It is assumed that the attrition rate for the study will be negligible. Study enrollment will continue during each interim analysis until a decision is reached to stop enrollment based on the interim

Biosense Webster, Inc

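### A phrenic paralysis documented by day 7 drops out of the primary safety analysis if the 3-month status is missing, and the plan has no rule for that case

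*SAP*

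**What the plan says.** Protocol 9.1.3 gives the general rule: "A Primary AEs is an event listed in Table 9.1.3A which occurs within the first week (7 days) following an ablation procedure". For one component, Table 9.1.3-A adds a later condition: "diaphragmatic paralysis/phrenic nerve palsy will be considered a Primary AE if specified symptoms have not improved at the 3- month visit".

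SAP 11.4.2 sets the missing-data rule for the final safety analysis, and SAP 11.4.4 has the same rule. Anyone with incomplete follow-up for the "endpoint assessment will be excluded in the primary analysis unless they have experienced a PAE". The length of follow-up is not given in days, but SAP 11.4.3 times the analysis after the 3-month evaluation, and section 3 of the SAP Appendix calls the endpoint a 3-month one.

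SAP 6.1.1 lists phrenic nerve paralysis without an asterisk and without the 3-month condition. Protocol 3.2.1 has the same list but sends the reader to Section 9.1.3 for definitions. Neither document says how to classify a paralysis found by day 7 when the 3-month status is missing.

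SAP 11.4.5 plans two safety sensitivity analyses: a tipping-point analysis in the mITT population, and a repeat in the Safety Population on available data with early PAEs carried forward. On losses, SAP 9 says: "It is assumed that the attrition rate for the study will be negligible".

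**The concern.** The exception for subjects who have already had a PAE keeps observed harm in the numerator even when later follow-up is lost. It works for tamponade, stroke, TIA and major bleeding, which count when they occur. It does not work for phrenic paralysis, because that event is not yet a PAE when it is found. Without a 3-month finding the condition in Table 9.1.3-A cannot be met, so the exception does not apply and the subject is excluded.

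Where the missing status would have been no improvement, the exclusion favours the device. Loss may also be related to the injury, since Protocol 4.3.1 lists an adverse event as a reason to end participation. The component is a live one: the only primary event in the feasibility study was a diaphragmatic paralysis (Protocol 1.2.3). The pass limit is a whole number of events, so a single classification can decide a close result.

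**Working it through.** **Inputs from the documents.** Goal 15%, exact binomial test, one-sided 5% (SAP 11.4.2). Looks at 80, 130 and 180, maximum 230, stopping bounds 90% and 6.5%, uniform prior (SAP 11.4.3). **Assumed, because the documents give no figure:** 3-5% of subjects with early paralysis, and 5-10% of those without a 3-month status.

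**1. Reproduce the plan's figure.** The Appendix states: "an anticipated rate of at most 9.5% for the primary safety endpoint, 230 subjects will be sufficient to obtain at least 80% power". The limit is the largest c with P(X ≤ c | n, 0.15) ≤ 0.05. At n = 230, c = 25, with exact alpha 4.40%. Power is P(X ≤ 25 | 230, 0.095) = 79.7%, which agrees with 80% to rounding.

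**2. Effect of dropping one injured subject.** The upper bound is the 95th percentile of Beta(x + 1, n − x).

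| Counted as PAE | Upper bound | Dropped | Upper bound |
|---|---|---|---|
| 7/80 | 15.81% | 6/79 | 14.44% |
| 13/130 | 15.43% | 12/129 | 14.64% |
| 19/180 | 15.10% | 18/179 | 14.55% |
| 26/230 | 15.34% | 25/229 | 14.91% |

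At each size, one dropped subject turns a fail into a pass only if the count is exactly one above the limit (6, 12, 18 or 25).

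**3. Expected number affected** = N × early paralysis rate × missing share.
- N = 80: 80 × 0.03 × 0.05 = 0.12, up to 80 × 0.05 × 0.10 = 0.40.
- N = 230: 230 × 0.03 × 0.05 = 0.35, up to 230 × 0.05 × 0.10 = 1.15.

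**4. How often the final count is one above the limit.** I simulated the adaptive rule in simplified form: 100,000 trials per setting, with 10, 20 or 25 subjects incomplete at each look and extra enrolment during looks ignored. The probability of ending exactly one above the limit, at whatever size the trial stops, was:
- true rate 9%: 3.8-4.3%
- true rate 7%: 1.2-1.3%
- true rate 5%: 0.2-0.3%

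The simulation is approximate. Its power at 9% is 82-83%, against 80.05% in Appendix Table 2.a.

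**5. Both conditions together, at a true 9% rate.** With N = 230 and a Poisson approximation, the chance of at least one affected subject is 1 − exp(−0.35) = 0.30 to 1 − exp(−1.15) = 0.68. Treating the two conditions as independent, 0.04 × 0.30 = 1.2% and 0.04 × 0.68 = 2.7%. So in roughly 1-3% of trials the two rules would give different verdicts, and in fewer at lower true rates.

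**6. Type I error, worst case.** Fix N = 230, set the true rate at 15%, and suppose every dropped subject would have been a PAE. If q is the phrenic PAE rate and m the share without a 3-month status, a subject is dropped with probability d = q × m, and the remaining subjects have rate (0.15 − d)/(1 − d). With q = 2.6% (an assumption set at the feasibility rate of 1 in 39), the error goes from 4.40% to 4.91%, 5.44% and 6.49% for m = 5%, 10% and 20%.

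**The case against.** **Status may be known without the visit.** Protocol 9.3 requires adverse events to be followed until resolved. Protocol 4.3.2 requires follow-up of a subject withdrawn for an adverse event until it is resolved or stable, and three calls and a certified letter before a subject is declared lost. This stands, and it makes a truly unknown status less likely. But the SAP does not say that off-visit information may settle the classification.

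**The injury may have improved.** A reader might infer that the plan discards a known, unresolved injury. The documents do not support that. Status at a missed visit is unknown, and Protocol 1.4.1 describes paralysis after second-generation cryoballoon ablation as transient in most cases. Dropping a subject who had in fact improved only shrinks the denominator, which works slightly against the device.

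**The sensitivity analyses would show it.** The tipping-point analysis covers the case where this subject is a PAE, so a verdict resting on one such subject would be visible. But success is decided by the primary bound. The carry-forward in the Safety Population helps only if the paralysis already counts as a PAE, which Table 9.1.3-A leaves open.

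**The chance of a critical count looks larger than it is.** A reader might take the plain binomial probability of 7 events in 80 at a 9% rate, 15.5%, as the chance that one subject decides the trial. That ignores the stopping rule: seven events at 80 normally send the trial on to 130. In the simulation, stopping at 80 and ending with 7 events had probability 0.4-1.0%.

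**Counting unknown as an event is a choice.** This is fair. It is a worst-case imputation for one component, and either count could be primary. The conservative count suits a safety test whose exclusion rule already tries to keep observed harm.

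**Conclusion.** The gap is real and worth closing, but small. On the plain reading, a day-7 paralysis without a 3-month status leaves the primary analysis. If SAP 6.1.1 is instead read as counting paralysis at onset, the documents support two classifications of the same subject, and a rule is needed either way.

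A reader might infer that the primary test is biased as it stands, or that its type I error exceeds 5%. Neither is established. The rate could be biased towards the device if such subjects occur and had not improved. The type I figures above 5% need a fixed sample size, at least about 10% missing status at the assumed 2.6% phrenic rate, and every dropped subject being a true PAE, whereas the plan assumes negligible attrition. The size of the effect rests on the assumed paralysis and missing-status rates and on the simplified simulation. The step from fail to pass in the table is exact.

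**What to change.** In SAP 11.4.2 and 11.4.4, state that for the primary analysis a phrenic paralysis with onset within 7 days is kept and counted as a PAE unless improvement by 3 months is documented from any source, including adverse event follow-up outside the visit under Protocol 4.3.2 and 9.3. Report the count with such subjects excluded as a sensitivity analysis. Align Protocol Table 9.1.3-A and SAP 6.1.1 with this wording, since the present definition is tied to the visit and an SAP sentence alone would leave the two documents in conflict.

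The change affects classification only and needs no new visits, data or change in patient care. Its cost is that the observed PAE rate may rise by about one subject, who may in fact have recovered, and in a close result that could turn a pass into a fail.

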11.4.3 Interim Analysis

Sample size selection interim analyses will be performed when the mITT population reaches 80, 130, and 180 subjects. Safety outcome at 30 days will be used as a proxy for the primary safety endpoint at each interim.

At the time of each interim analysis, predictive probabilities of success for safety will be calculated once using the current sample size and another time using the maximum sample size allowed. A uniform prior distribution will be assumed for the safety rate at the first interim analysis, and the distribution will be updated with the observed data at each subsequent interim analysis. The number of failures for the primary safety endpoint in subjects with incomplete information will be assumed to follow a beta-binomial distribution. The predicted number of failures for the primary safety endpoint will be estimated from these beta-binomial distributions. The observed and predicted number of failures will provide estimates for the anticipated study outcomes with the sample size at the time of the interim analysis and the maximum sample size allowed. The Bayesian predictive probability of success for safety for each case will be calculated from these estimates.

Enrollment will be stopped if the predictive probability of success for safety with the current sample size is greater than 90% or if the predictive probability of success for safety using the maximum sample size allowed is less than 6.5%. Otherwise, enrollment will continue until the 230th subject in the mITT population is recruited. Regardless of whether enrollment stops at one of the interim analyses or continues to a sample size of 230 subjects, the primary safety and effectiveness analyses will be conducted after all subjects have completed their 3-month post-procedure evaluation.

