### **14.7.1 Adaptive Sample Size Determination**

In this section, an incidence of any primary adverse events will be referred to as a failure for the primary safety endpoint. The methods described in Broglio et al. will be used for adaptive determination of the sample size.

At the time of each interim analysis, predictive probabilities of success for safety will be calculated once using the current sample size and another time using the maximum sample size allowed. A uniform prior distribution will be assumed for the safety rate at the first interim analysis, and the distribution will be updated with the observed data at each subsequent interim analysis. The number of failures for the primary safety endpoint in subjects with incomplete information will be assumed to follow a beta-binomial distribution. The predicted number of failures for the primary safety endpoint will be estimated from these beta-binomial

distributions. The observed and predicted number of failures will provide estimates for the anticipated study outcomes with the sample size at the time of the interim analysis and the maximum sample size allowed. The Bayesian predictive probability of success for safety for each case will be calculated from these estimates.

Enrollment will be stopped if the predictive probability of success for safety with the current sample size is greater than 90% or if the predictive probability of success for safety using the maximum sample size allowed is less than 6.5%. Otherwise, enrollment will continue until the 230th subject is recruited. The Statistical Analysis Plan contains details on the timing of the interim analysis and estimation of the predictive probability of success at the interim looks. Regardless of whether enrollment stops at one of the interim analyses or continues to a sample size of 230 subjects, the primary safety and efficacy analyses will be conducted after all subjects have completed their 3-month post-procedure evaluation.

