6 STUDY ENDPOINTS

6.1 Primary Endpoints and Associated Hypotheses

6.1.1 Primary Safety Endpoints

The primary safety endpoint is the incidence of early onset Primary Adverse Events (PAEs) (within seven (7) days of the initial mapping and ablation procedure). PAEs include the following AEs.

Death*	Stroke/CVA
Atrio-Esophageal Fistula*	TIA
Myocardial Infarction	Phrenic Nerve Paralysis
Cardiac Tamponade/perforation	Pulmonary Vein Stenosis*
Thromboembolism	Major Vascular Access Complication/Bleeding

* Device or procedure related death, pulmonary vein stenosis and atrio-esophageal fistula that occur greater than one week (7 days) and less than or equal to 90 days post procedure are considered and analyzed as primary AEs.

The PAE rate will be compared against the performance goal of 15% by testing the following hypotheses:

$$H_0: p_S \geq 0.15 \quad \text{vs.} \quad H_A: p_S < 0.15,$$

where p_S is the PAE rate.

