results. Due to the continued enrollment during this time, we expect an additional 5 to 6 subjects enrolled into the study. These additional subjects will be included in the primary analyses and should account for the potential subject attrition.

3. Adaptive Sample Size Determination

In this section, an incidence of any primary adverse events will be referred to as a failure for the primary safety endpoint. Sample size selection interim analyses will be performed when 80, 130, 180, and 230 evaluable subjects (excluding roll-in) are available for the primary safety endpoint analysis. Safety outcome at 30 days will be used as a proxy for the 3-month primary safety endpoint at each interim. The final safety analysis will be based on complete follow-up for the primary safety endpoint for all evaluable patients. Predictive probabilities of success will be used to determine whether the sample size at each interim analysis will be sufficient or if the trial enrollment will continue. Sample size simulations were performed using performance goals of 15% and 80% respectively for the safety and effectiveness endpoint rates.

At the time of each interim analysis, predictive probabilities of success for safety will be calculated once using the current sample size and again using the maximum sample size allowed. A uniform prior distribution will be assumed for the safety rate at the first interim analysis, and the distribution will be updated with the observed data at each subsequent interim analysis. The number of failures for the primary safety endpoint in subjects with incomplete information will be assumed to follow a beta-binomial distribution. The predicted number of failures for the primary safety endpoint will be estimated from these beta-binomial distributions. The observed and predicted number of failures will provide estimates for the anticipated study outcomes with the sample size at the time of the interim analysis and the maximum sample size allowed. The Bayesian predictive probability of success for safety for each case will be calculated from these estimates. No primary effectiveness endpoint analyses will occur until final sample size selection based on the primary safety endpoint has taken place.

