Enrollment will be stopped if the predictive probability of success for safety with the current sample size is greater than 90% or if the predictive probability of success for safety using the maximum sample size allowed is less than 6.5%. Otherwise, enrollment will continue until the 230th subject is recruited. The Statistical Analysis Plan will contain details on all planned analyses. Regardless of whether enrollment stops at one of the interim analyses or continues to a sample size of 230 subjects, the primary analyses of the primary safety and effectiveness endpoints will be conducted after all subjects have completed their 3-month post-procedure evaluation.

4. Power and Type-I Error Simulations

Trial simulations were performed to estimate the Type-I error rate and the power for the success of the safety endpoint under a range of assumptions for the true safety rate and the assumed enrollment schedule. Three different enrollment schedules were considered for the simulations

corresponding to realistic, conservative, and aggressive enrollment schedules based on logistical considerations:

Table 1 Assumed Enrollment Schedules

	Expected number of patients per month													
	M1	M2	M3	M4	M5	M6	M7	M8	M9	M10	M11	M12	M13	M14
Realistic	1.7	3.4	5.1	8.5	11.9	17.0	20.4	23.8	25.5	25.5	25.5	25.5	25.5	25.5
Conservative	1.2	3.0	6.0	10.5	15.0	18.0	21.0	22.5	22.5	22.5	22.5	22.5	22.5	22.5
Aggressive	2.5	5.0	10.0	15.0	22.5	30.0	35.0	37.5	37.5	37.5	37.5	37.5	37.5	37.5

Table 2.a provides the estimated power as a function of the true safety rate under the realistic enrollment schedule based on 10,000 simulations for each scenario. In addition, the table provides the proportion of times we expect to stop enrollment at each interim look either for adequate sample size or for futility. Assuming a true safety rates of 0 to 9.0%, the power for showing success for the safety endpoint is estimated to be greater than or equal to 80.0%. For a safety rate of 9.5% this power decreases to approximately 73.0%. With a true effectiveness of rate of 96.0% and a performance goal of 80.0%, a minimum of 80 patients will provide 99.9% power for meeting the primary effectiveness endpoint. Therefore, the power estimates for the primary safety endpoint closely estimate the overall power of the study.

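### Does the SAP need a rule for scoring a phrenic nerve palsy that is still unresolved at day 30 when an interim look is taken?

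*SAP*

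**What the plan says.** SAP 11.4.3 sets the interim outcome: "Safety outcome at 30 days will be used as a proxy for the primary safety endpoint at each interim". The simulation report in SAP section 12 is more explicit about what is replaced: "Safety outcome at 30 days will be used as a proxy for the 3-month primary safety endpoint at each interim".

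Subjects without a settled outcome are predicted: "The number of failures for the primary safety endpoint in subjects with incomplete information will be assumed to follow a beta-binomial distribution". SAP 11.4.4 describes them in one way only, noting that at a look "some subjects will not have completed the full 30-day follow-up for their safety evaluation".

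Two parts of the endpoint extend past day 30.
- Protocol Table 9.1.3-A: "diaphragmatic paralysis/phrenic nerve palsy will be considered a Primary AE if specified symptoms have not improved at the 3- month visit". Protocol 8.3 puts that visit at day 76-104.
- SAP 6.1.1: related death, pulmonary vein stenosis and atrio-esophageal fistula after day 7 and "less than or equal to 90 days post procedure are considered and analyzed as primary AEs".

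Protocol 14.7.1 says the SAP holds "details on the timing of the interim analysis and estimation of the predictive probability of success at the interim looks". Appendix section 4 of the SAP reports simulations "under a range of assumptions for the true safety rate and the assumed enrollment schedule", and varies nothing else. Both documents run the primary analyses only after every subject has completed the 3-month evaluation.

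**The concern.** A symptomatic palsy at day 30 is not yet a primary adverse event, and it is not ruled out as one either. The protocol sends the reader to the SAP for the estimation details, and the SAP gives no scoring for this case. It also does not say that the 3-month classification later overrides the 30-day status, or how a related death, stenosis or fistula on days 31-90 enters a look.

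The event is plausible. The only primary adverse event in the feasibility study (Protocol 1.2.3) was a diaphragmatic paralysis.

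At stake is the enrolment decision. The predictive probability can stop enrolment because the sample is large enough, or end it for futility. If the same data can give stop or continue depending on a choice made at the look, part of the adaptive rule is not prespecified. The published operating characteristics also contain no run in which the 30-day and 3-month outcomes disagree.

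**Working it through.** **Inputs.** Goal 15%, exact one-sided 5% test, looks at 80/130/180 with maximum 230, stop above 0.90 at current N, futility below 0.065 at N=230, uniform prior (SAP 6.1.1, 7, 11.4.3); realistic accrual (SAP appendix, Table 1).

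**Critical counts.** The largest c with P(Bin(N, 0.15) ≤ c) ≤ 0.05 is 6/80, 12/130, 18/180 and 25/230.

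**Reproducing the plan's figures.**
- Fixed design: P(Bin(230, 0.095) ≤ 25) = 0.797, against the stated 80%.
- Feasibility posterior: a uniform prior with 1 event in 39 gives Beta(2, 39), and P(rate ≤ 9%) = 0.886, as stated.
- Adaptive design at a 9% rate, no 30-day/3-month disagreement, events counted as they occur: power 0.80 (SAP 0.8005) and futility stops 14.7% (SAP 0.0851 + 0.0311 + 0.0243 = 14.05%). A variant using only subjects past day 30 gives power 0.82 to 0.83, so the SAP's simulation details are matched only approximately.

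**Effect of one palsy on fixed data.** With x failures among n settled subjects and m = N − n to predict, the predictive probability is P(BetaBin(m; 1+x, 1+n−x) ≤ c − x). For futility, c = 25 and m = 230 − n. Realistic accrual leaves about 25.5 × 30/30.4 ≈ 25 subjects short of day 30 at the later looks; 26 is used.

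N=130, 8 other failures, 104 subjects past day 30 including the palsy:
- failure: x=9, n=104, P(BetaBin(26; 10, 96) ≤ 3) = 0.760, continue
- non-failure: x=8, n=104, P(BetaBin(26; 9, 97) ≤ 4) = 0.915, stop
- incomplete: x=8, n=103, P(BetaBin(27; 9, 96) ≤ 4) = 0.901, stop

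| Look, other failures, short of day 30 | Rule | Failure | Incomplete | Non-failure |
|---|---|---|---|---|
| 80, 3, 23 | >0.90 | 0.688 | 0.889 | 0.904 |
| 130, 8, 26 | >0.90 | 0.760 | 0.901 | 0.915 |
| 180, 13, 26 | >0.90 | 0.886 | 0.957 | 0.964 |
| 80, 9, 23 | <0.065 | 0.032 | 0.072 | 0.080 |
| 130, 14, 26 | <0.065 | 0.062 | 0.121 | 0.131 |
| 180, 20, 26 | <0.065 | 0.031 | 0.077 | 0.085 |

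**How narrow this is.** Failure scoring with k other failures is arithmetically non-failure scoring with k+1. At N=130 with 7 others, failure scoring therefore gives 0.915 and both scorings stop; with 9 others, non-failure scoring gives 0.760 and both continue. For a single palsy, the two scorings disagree at exactly one count for each rule at each look. Results for incomplete scoring are less stable: at N=80, 22 rather than 23 subjects short of day 30 moves 0.889 to 0.904, and at N=130, 27 rather than 26 moves 0.901 to 0.887.

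**Frequency and power.** The documents give no share of palsies open at day 30, so 0.5, 1 and 2 percentage points are assumed. Expected open palsies at a look are then 0.16-0.25, 0.33-0.5 and 0.65-1.0. At a 9% rate the enrolment decision differs between failure and incomplete scoring in about 6%, 12% and 24% of trials, and between non-failure and incomplete in about 1%, 2% and 4%. Power when the palsies later resolve (zero-disagreement value 0.80):

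| Scoring | 0.5 | 1 | 2 |
|---|---|---|---|
| Failure | 0.78 | 0.77 | 0.73 |
| Incomplete | 0.80 | 0.80 | 0.79 |
| Non-failure | 0.80 | 0.80 | 0.80 |

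If the palsies are later confirmed, incomplete and non-failure scoring both give 0.81/0.82/0.82. Stopping for adequate sample size and then failing occurs in 0.4%/0.8%/2.3% and 0.5%/1.0%/3.1% of trials. At a 5% rate power is at least 0.98 under all three scorings, provided the 3-month classification replaces the 30-day status. Events on days 31-90, counted when they occur (0.5 or 1 point), leave power at 0.81.

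A harsher run with the completers-only variant assumes 2 points persistent plus 2 resolving: power 0.78 (failure), 0.79 (non-failure) and 0.81 (incomplete). With 4 plus 4 it is 0.70, 0.72 and 0.75. In that case 8% of subjects have a palsy open at day 30, more than the total palsy incidence Protocol 1.4.1 cites for hot balloon (<4%) or laser balloon (≤6%). All three scorings lose power there, so most of the loss comes from the proxy itself.

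**Type I error.** With incomplete scoring and up to 2 points, one model gives at most 4.6% (baseline 3.9%) and the completers-only variant 5.4% (baseline 5.0%). The harsher run gives 3% to 5.4% (baseline about 5.2%). The SAP reports 4.7%. None of these shows clear inflation.

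**The case for a change.** The best case for acting is that an adaptive stopping rule in an unmasked single-arm study should leave nothing to be decided at the look. The protocol promises the details in the SAP, one event of the type seen in the feasibility study can reverse a decision, and a few sentences would close the gap. If 2 points is realistic, failure and incomplete scoring disagree in about a quarter of trials at a 9% rate.

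The gap stands: failure or non-failure is not written down. Less stands of its reach. SAP 11.4.4 describes incomplete subjects only as those short of 30 days, so a subject past day 30 is naturally complete under the proxy, and the practical question is the two-way one. Scoring a failure can be defended by applying the symptom criterion at day 30, but it counts an event that the protocol definition has not yet made a primary adverse event. The other two scorings respect that definition and perform almost alike.

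A written rule would also need care. One covering every palsy not yet classified at 3 months would hold as unsettled those that improved before day 30, and Protocol 1.4.1 says most cryoballoon palsies recover during the procedure or by discharge. The looks are run by an independent statistician with a data monitoring committee under a charter that was not supplied, so whether a convention already exists cannot be determined.

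**Conclusion.** No change to the plan follows. The SAP leaves a small operational detail open, and an independent statistician holding the event definition and the 30-day proxy can fill it sensibly. Using a 30-day proxy for a 3-month endpoint is a fair trade-off in a design that must decide during accrual.

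The final analysis is unaffected: every subject is classified at 3 months before the exact test. The consequence is limited to when enrolment stops and, through that, to power. At a 9% rate, for palsies that later resolve, power is 0.79 to 0.80 under either scoring that respects the definition, against 0.80 with no disagreement. It is 0.78 to 0.73 under failure scoring, a loss of 2 to 7 points. At 5% it is at least 0.98 throughout. The feasibility rate was 2.6% (1 in 39).

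These figures rest on assumed open-palsy rates of 0.5 to 2 points, on the realistic accrual schedule, on the 3-month classification replacing the 30-day status, and on simulations that match the SAP tables only approximately. The fixed-data values do not depend on the simulations. A run with 30-day/3-month disagreement would be informative but would alter no planned decision rule or test.
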